### 4.2 Secondary Efficacy Endpoints

• The secondary efficacy variable is the difference between treatment groups in Subject Global Impression of Severity (SGIS) scores at Visit 11. If Visit 11 is missing, the last available SGIS will be used.

### 4.3 Additional Efficacy Endpoints

## 4.4 Exploratory Endpoints

Exploratory efficacy endpoints include:

•

Version 9.0

21Sep2017

\_

### 4.5 Safety Endpoints

- Adverse Events
- Vital signs resting pulse, sitting systolic and diastolic blood pressure, respiration, and body temperature
- Clinical laboratory tests
- 12 lead electrocardiogram (ECG)
- Neurological examinations
- Suicidality assessments
- Exposure and compliance
- •
- Physical examinations

### 4.6 Study Definitions

## **4.6.1 Study Day**

For purposes of describing days on study drug in data listings, data will be assigned a study day, relative to the start at Visit 2, according to the following rules (this numbering of days differs from the Study Days as described in the protocol):

For events that occurred after Visit 2:

Study Day = visit date 
$$-$$
 date of Visit  $2 + 1$ 

For events prior to Visit 2:

Study Day = visit date 
$$-$$
 date of Visit 2

Visit numbers as designated on the study eCRFs (Electronic Case Report Forms) will be used. For selected parameters, visit windows will also be calculated for use in descriptive statistics by time.

The baseline time point for different assessments will be defined in the respective sections. For evaluations that are collected at multiple occasions prior to initiation of study treatment, the latest evaluation will be considered the "Baseline" evaluation for analysis.

Unless indicated otherwise, change from baseline (CFB) will be calculated as follows:

• CFB = Value at Visit - Baseline

#### 5. STATISTICAL ANALYSIS GENERAL CONSIDERATIONS

#### **5.1 Analysis Populations**

#### **Safety Population:**

The safety population will be all subjects who received at least one dose of
. Subjects who discontinue having received only (in Part 1) and are not available for evaluation at Visit 2 will not be included in the safety population. The Safety Population for Part 3 will be based on only those Safety subjects who received a dose of randomized study drug at Visit 7.

#### **Intent-to-Treat (ITT) Population:**

The ITT population will be defined as all subjects who are randomized to double-blind study drug at Visit 7 and subsequently received at least one dose of study medication, and have one subsequent modified Ashworth and CGIC score at the same assement.

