	For the primary efficacy analysis, subjects who provide modified Ashworth and CGIC scores at Visit 11 and meet the treatment failure criterion at Visit 11, or who have met the treatment failure criterion at any prior visit will be classified as being treatment failures. All other subjects will be classified as not being treatment failures.
Secondary Efficacy Outcomes:	Subject Global Impression of Severity (SGIS)
Safety Assessments:	
 
Treatment Emergent Adverse Events
 
Daytime sedation
 
Vital Signs (seated blood pressure and pulse)
 
Clinical laboratory tests
 
12 Lead ECG
 
Physical examination and neurological evaluation
 
Columbia – Suicide Severity Rating Scale
 

Treatments:	•
Study Population:	Subjects aged 18 years and above with spasticity due to multiple sclerosis with acceptable symptom control
Number of Subjects:	Approximately 300 subjects will be enrolled to ensure that at least 240 subjects are randomized at the beginning of
Number of Centers:	Up to 35 centers
Setting:	Out-patient clinics
Statistical Methods:	Efficacy Analyses: The primary efficacy analysis will be performed on an intent-to-treat (ITT) population, defined as all subjects who were randomized to double-blind study drug at Visit 7 and subsequently received at least one dose of study medication.
	).
	A per protocol (PP) population may also be analyzed (if it differs from the ITT population overall by more than 10% in sample size), defined as all ITT population subjects who had at least one on-treatment assessment in Part 3, and did not have any major protocol violation (such as poor compliance).

Confidential Page 3 of 67

Confidential Page 4 of 67

used medications.

Subject listings will be provided for all safety parameters as well as recently and concurrently

Table 1: STUDY DESIGN AND SCHEDULE OF ASSESSMENTS

		1 a	DIC 1. 510	DESIGN I	ALID SCHED	ULE OF ASS	ESSIVIE VIS					
Visit	S	Run- In		Open-La	abel				Double-		bo-Controlle ation	d Down-
	Screening											
	(-14 days)	Visit 1	Visit 2	Visit 3	Visit 4	Visit 5	Visit 6	Visit 7	Visit 8	Visit 9	Visit 10	Visit 11
Week												
Informed consent	×		_			_						
Demographics	×											
Medical and medication	×	×										
history												
Physical examination 	×											× 
Neurological examination	×											× 
Vital sign measurements 	×	×	×	×	×	×	×	×	×	×	×	×
		x										

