#### 10.3 Study Populations

#### 10.3.1 Efficacy Populations

#### 10.3.1.1 ITT Population

The ITT population will be defined as all subjects who are randomized to double-blind study drug at Visit 7 and subsequently received at least one dose of study medication.

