#### 10.4.3.2 Additional Analyses of the Primary Efficacy Outcome

#### 10.4.3.2.1 Sensitivity Analyses

Severa	Several sensitivity analyses		
	The sensitivity analyses are as follows:		
(a)			
(b)			
(c)			
(d)			
(u)			

Confidential Page 56 of 67

[figure not shown]

Confidential Page 57 of 67

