#### 6.2.1.3 Derivation of Primary Endpoint

The primary efficacy variable is the proportion of subjects who become a Treatment Failure during the double-blind randomized withdrawal part (Part 3). Using the primary efficacy variable, the CRO will perform a determination of failures (the blinded failure analysis). A subject's response status will be determined after database lock, but prior to unblinding the data. A subject who meets the following criterion will be considered a treatment failure:

• A CGIC of ≥ 5 ("minimally worse" to "very much worse") and at least one movement with a ≥ 1 unit increase in MAS from Baseline (A change from 1 to 1+ and 1+ to 2 will be counted as a 1-unit change)

The MAS at a given visit will be	e recorded for each of the	12 movements measured.	

For the Treatment Failure analysis, subjects who provide MAS and CGIC scores at Visit 11 and meet the treatment failure criterion at Visit 11,

21Sep2017

All other subjects will be classified as not being Treatment Failures.

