### 6.2.1.5 Primary Efficacy Analysis

The primary efficacy analysis will be performed using the intent-to-treat (ITT) population.

The primary efficacy analysis will be carried out using a two-sided test at the alpha=0.05 level of significance.

. Alternate approaches to handling missing data are discussed in Section 6.2.1.6.

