### 6.2.1.6 Sensitivity Analysis of the Primary Efficacy Analysis

Several sensitivity analyses of the impact of missing data on the primary efficacy endpoint will be performed. First, the primary efficacy analysis will be repeated in the PP population if it differs in size from the ITT population by more than 10% overall. In addition, the primary efficacy analysis will also be performed (using the ITT population) with different assumptions regarding the response status of a subject with missing data.

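### The SAP's ITT population requires a post-randomization assessment that the protocol's ITT does not, and no visible analysis restores the subjects it removes

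*SAP*

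**What the plan says.** Protocol section 10.3.1.1 defines ITT as "all subjects who are randomized to double-blind study drug at Visit 7 and subsequently received at least one dose of study medication", and the synopsis says the same. In the protocol, a requirement for an on-treatment assessment appears only in the per-protocol (PP) definition (section 10.3.1.2).

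SAP section 5.1 starts from the same two conditions for ITT and adds that the subject must "have one subsequent modified Ashworth and CGIC score at the same assement". SAP section 2 states that the SAP prevails where it differs from the protocol's statistical section. SAP section 6.2.1.5 then states: "The primary efficacy analysis will be performed using the intent-to-treat (ITT) population".

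On classification, the protocol synopsis describes who counts as a treatment failure and ends: "All other subjects will be classified as not being treatment failures". SAP section 6.2.1.3 closes with almost the same sentence, "All other subjects will be classified as not being Treatment Failures", but text is missing just before it, so its exact scope there cannot be seen.

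On missing data, SAP section 6.2.1.6 says the primary analysis will be repeated ("using the ITT population) with different assumptions regarding the response status of a subject with missing data"). The list that protocol section 10.4.3.2.1 introduces with "The sensitivity analyses are as follows" is redacted, as is any detail after the SAP's general statement.

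**The concern.** Whether a subject has a joint modified Ashworth and CGIC score after Visit 7 is known only after randomization, and treatment may influence it. In a randomized-withdrawal trial, a subject moved to placebo may leave early because spasticity returns. Clinical worsening or loss of efficacy is one of the discontinuation reasons listed in SAP section 6.1.1. Removing such subjects means that randomization no longer fixes the primary denominators, yet the result would still be reported as ITT.

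Determining the populations under blind (SAP sections 5.5 and 5.6) prevents selection driven by known treatment. It does not prevent one arm from losing more subjects than the other before a joint score is obtained. The bias could favour either arm.

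**Working it through.** **Comparison of definitions**

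| Condition | Protocol ITT | SAP ITT | SAP PP |
|---|---|---|---|
| Randomized at Visit 7 | yes | yes | yes |
| At least one dose | yes | yes | yes |
| Later joint Ashworth and CGIC score | no | yes | yes |
| No important deviation | no | no | yes |

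The subjects at issue are those randomized and dosed who have no joint score at any assessment after Visit 7. Under the protocol they are analysed as non-failures; under the SAP they are not analysed.

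**Does any visible analysis restore them?** The missing-data analyses in SAP section 6.2.1.6 run inside the SAP's ITT. The PP set requires the same joint score, so it lies within the SAP's ITT. The time-to-dropout table and figure (14.2.20 and 14.2.20.1) do not help: the table is specified on ITT, so it omits dropouts who never had a joint assessment. The disposition summary and the all-enrolled listings can show who was excluded, but they do not analyse them.

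**Size, as an illustration.** The plan gives no figure to reproduce here: the allocation ratio, failure rates and primary test are redacted. The only documented input is at least 240 randomized (SAP section 3.2.1). Assumptions: 120 per arm, with 36 active and 50 placebo failures among assessed subjects. The uncorrected chi-square is equivalent to z = (pP − pA) / √[p(1−p)(1/nA + 1/nP)], where p is the pooled proportion.

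Worked case, 2 active and 6 placebo subjects unassessed:
- SAP set: 36/118 = 30.5% v 50/114 = 43.9%, p = 86/232 = 0.371. z = 0.1335/0.0634 = 2.10, two-sided p=0.035.
- Protocol ITT: 36/120 = 30.0% v 50/120 = 41.7%, p = 86/240 = 0.358. z = 0.1167/0.0619 = 1.88, two-sided p=0.060.

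All cases (difference in points, uncorrected p, Fisher p in brackets):

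| Unassessed: active, placebo | SAP set | Protocol ITT, unassessed = non-failure | All randomized and dosed, unassessed = failure |
|---|---|---|---|
| 2, 2 | 11.9; 0.058 (0.078) | 11.7; 0.060 (0.080) | 11.7; 0.062 (0.083) |
| 4, 4 | 12.1; 0.057 (0.077) | 11.7; 0.060 (0.080) | 11.7; 0.064 (0.085) |
| 2, 6 | 13.4; 0.035 (0.042) | 11.7; 0.060 (0.080) | 15.0; 0.017 (0.024) |
| 6, 2 | 10.8; 0.089 (0.103) | 11.7; 0.060 (0.080) | 8.3; 0.186 (0.234) |

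A second assumed base case, 25 active and 40 placebo failures, shows the opposite crossing. With 8 active and 2 placebo subjects unassessed, the SAP set gives 11.6 points (p=0.051) and the protocol's ITT gives 12.5 points (p=0.029).

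**How narrow is the range in which the conclusion changes?** Take the 2-and-6 case with 36 active failures and placebo failures varied from 48 to 52. The two sets fall on opposite sides of 0.05 only at 49–50 placebo failures (uncorrected) or 50–51 (Fisher or continuity-corrected).

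**Side effect on the PP trigger.** The PP repeat runs only if PP differs from ITT by more than 10%. Suppose 240 are randomized and dosed, 10 are unassessed, and 20 others have important deviations, so PP = 210. Against the protocol's ITT the gap is 30/240 = 12.5%, and the repeat runs. Against the SAP's ITT it is 20/230 = 8.7%, and it does not.

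**The case against.** The strongest reply is that the group is probably very small. A subject is lost from the SAP's set only with no joint score at Visits 8 to 11 or at an exit examination. Both scores are due weekly, earlier visits are allowed, and final-visit examinations are expected for early leavers wherever feasible (protocol section 7.1.1). SAP Table 2 and section 6.1.8 show that Part 3 involves down-titration, so placebo subjects may still be tapering before Visit 8. That would limit early arm-related loss, although the schedule is redacted. This stands as a limit on likely size.

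The illustrative p-values also depend on chosen inputs near the threshold. With a milder imbalance of 1 active and 3 placebo, 36 active failures, and placebo failures varied from 44 to 57, the two sets straddle 0.05 at only one count (50 uncorrected; 51 corrected or Fisher). This also stands: no effect on the actual result is demonstrated.

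A restoring analysis may sit in the redacted lists. That cannot be ruled out, but the one visible SAP sentence on missing data confines those analyses to the SAP's ITT.

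The protocol's default is imperfect too. It counts an early leaver for loss of efficacy as a success, which could hide placebo failures. Relabelling the set as modified ITT and adding all-randomized-and-dosed analyses would be a less contestable change. That argues for the failure-imputed sensitivity analyses. It does not justify a primary set that departs from the protocol while keeping its name.

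Planned disposition counts by arm, the subject-flow figure and the all-enrolled failure listing make exclusions visible. They do not return anyone to an analysis.

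**Conclusion.** The concern holds and should be fixed. The difference in definition is explicit, the SAP's version governs, and it sets the denominator of the primary test. Confidence is high on the text and low on any numerical effect.

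The effect is negligible if exclusions are few or balanced. It matters only if they are unbalanced and the result lies close to 0.05. In the assumed 2-and-6 and 6-and-2 cases, the estimate moves from 11.7 points to 13.4 or 10.8. All failure and exclusion counts, and equal allocation, are assumptions. The case for change rests on the mismatch between protocol and SAP and the low cost of removing it.

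**What to change.** Before unblinding:

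1. In SAP section 5.1, delete the added condition ("have one subsequent modified Ashworth and CGIC score at the same assement") from the ITT definition, so that the primary analysis uses the protocol's ITT by randomized arm. State that the documents' existing non-failure default applies to subjects with no joint score. Keep the narrower set as a sensitivity analysis labelled modified ITT.
2. In SAP section 6.2.1.6, confirm that the withheld list includes, or add, analyses of all randomized, dosed subjects that count the unassessed (a) all as failures, and (b) as failures only where the recorded reason for leaving is clinical worsening or loss of efficacy. For scale, if 3 of the 6 placebo and 0 of the 2 active subjects in the 2-and-6 case left for worsening, (b) gives 36/120 v 53/120: 14.2 points, uncorrected p=0.023, Fisher 0.032.
3. Run Table 14.2.20 and Figure 14.2.20.1 on all randomized, dosed subjects.
4. In the disposition table, show by arm, with reasons, the subjects excluded from the modified ITT.

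The cost is SAP text edits, at most two extra sensitivity outputs, one table and one figure re-run, and added disposition rows. No new data or subjects are needed. The downside is that a few subjects receive an imputed outcome, non-failure is itself an assumption, and the primary estimate may become slightly less favourable.

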#### Per Protocol (PP) Population:

The per protocol (PP) population will be defined as all subjects who are randomized to double- blind study drug at Visit 7, subsequently receive at least one dose of study medication, have at least one subsequent modified Ashworth and CGIC score at the same assement, and do not have any important protocol deviations. Protocol deviations will be reviewed and subjects with important/not important violations will be identified prior to unblinding the clinical database.

In addition, concomitant medications will be reviewed for anti-spasticity medication use, its dose, and the timing relative to the in-clinic assessment. Adverse events will be reviewed in a similar fashion for confounding medical conditions. Finally, confounding due to changes in physiotherapy regimen will be assessed. In-clinic Ashworth assessments that are judged to be potentially confounded will be flagged. The analysis of the PP population will exclude such potentially confounded assessments.

Analyses of the primary efficacy endpoint will be repeated using the PP population if it differs in size from the ITT population in total number by more than 10% overall.

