#### 10.3.1.2 PP Population

The per protocol (PP) population will be defined as all subjects who are randomized to double-blind study drug at Visit 7, subsequently receive at least one dose of study medication, have at least one on-treatment assessment in Part 3, and do not have any major protocol violation (such as poor compliance). Protocol violations will be reviewed and subjects with major/minor violations will be

[figure not shown]
Confidential Page 53 of 67

identified prior to unblinding the clinical database. Subjects with a major protocol violation will be excluded from the analysis of the PP population.

In addition, concomitant medications will be reviewed for anti-spasticity medication use, its dose, and the timing relative to the in-clinic assessment. Adverse events will be reviewed in a similar fashion for confounding medical conditions. In-clinic Ashworth assessments that are judged to be potentially confounded will be flagged. The analysis of the PP population will exclude such potentially confounded assessments; response status will be solely on the basis of the clinician-rated CGIC.

Analyses of the primary efficacy endpoint will be repeated using the PP population if it differs in size from the ITT population in total number by more than 10% overall.

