#### 10.5 Unblinding

Breaking of the blind will occur at completion of the study.

At completion of the study, breaking of the blind will occur once the database has been cleaned and locked. Prior to final database lock, any major protocol violations, including changes in medication use or physiotherapy, and changes in medical condition will be identified. Only at that time will the Sponsor be granted access to the unblinded data.

At all other timepoints, breaking of the blind for any subject is discouraged and should be performed only under medical emergency conditions where the identification of the subject's treatment assignment is critical for proper medical care to be administered. In such circumstances, the Investigator must contact the Sponsor's Medical Representative (or designee) for permission to unblind. The representative will be available 24 hours a day. If a decision is made to unblind a subject's assignment, the Investigator will call the IVRS/IWRS statistician and request the subject's treatment group. Only the Investigator and the IVRS/IWRS statistician will be unblinded to the subject's treatment group and they will be responsible for documenting the time, date, and reason for code break.

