#### **6.1.3 Protocol Deviations**

A protocol deviation is any change, divergence, or departure from the study design or procedure defined in the protocol.

21Sep2017

A subset of the protocol deviations can be identified as an important protocol deviation as described below:

Important Protocol Deviation: A protocol deviation that might significantly affect the completeness, accuracy, and/or reliability of the study data or that might significantly affect a subject's rights, safety, or well-being. Important deviations include includion/exclusion criteria violations, cases where withdrawal criteria developed but the subject was not withdrawn, receiving the wrong treatment or incorrect dose, and receiving excluded concomitant medications.

Upon soft lock of the database, all documented protocol deviations in the study will be reviewed to identify all important protocol deviations by a data review team including representatives from clinical operations, medical, data management, and statistics, and sent to the sponsor for approval. Final decisions will be documented and databased.

Protocol violations during Part 3 will be summarized by treatment group for the ITT population, and all protocol violations and deviations will be listed.

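### SAP 5.1 omits the protocol's CGIC-only rule for per-protocol visits with a confounded Ashworth score, and in both documents the analysis that sets such scores aside runs only if a 10% difference in subject numbers is exceeded

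*SAP*

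**What the plan says.** **Treatment failure.** SAP 4.1 and 6.2.1.3 require two things together: CGIC of 5 or more, and at least one movement whose modified Ashworth score has risen by at least one unit from baseline. SAP 6.2.1.3 classes everyone else as not a failure. SAP 5.3 does not impute missing values unless stated.

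**Confounded Ashworth scores, protocol.** Protocol 10.3.1.2 flags in-clinic Ashworth assessments judged potentially confounded by anti-spasticity medication or medical conditions. It leaves them out of the PP analysis and adds that "response status will be solely on the basis of the clinician-rated CGIC".

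**Confounded Ashworth scores, SAP.** SAP 5.1 keeps the flagging and widens it: "Finally, confounding due to changes in physiotherapy regimen will be assessed". On use of the flags it says "The analysis of the PP population will exclude such potentially confounded assessments". The CGIC clause is absent, and no gap is visible at that sentence.

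**Precedence.** SAP 2 lets the SAP override the protocol's statistical section where the two disagree.

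**When the PP analysis runs.** The protocol synopsis, Protocol 10.3.1.2, SAP 5.1 and SAP 6.2.1.6 all make it conditional on PP and ITT differing by more than 10% in size.

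**Who is in each set under the SAP.** Both sets need randomisation, a dose and a paired score. ITT subjects must "have one subsequent modified Ashworth and CGIC score at the same assement"; PP subjects must "have at least one subsequent modified Ashworth and CGIC score at the same assement, and do not have any important protocol deviations".

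**The concern.** Setting an Ashworth score aside leaves a question that the plan must answer: what is the subject's status at that visit? The protocol answers it and the visible SAP text does not. Programmers following the two documents could report different PP failure counts from the same locked data. The SAP route also gives the excluded visit the value of a good outcome, which is an odd result for a score removed because it could not be trusted.

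The condition on running the analysis adds a second weakness. It measures how many subjects are lost from PP, whereas the confounding review works on individual assessments. Extensive confounding could be found under blind and still lead to no analysis that sets it aside. What is at stake is a supportive check on robustness, not the primary result.

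**Working it through.** **1. Status at a flagged visit**

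Inputs: the two-part criterion and default class (SAP 6.2.1.3), no imputation (SAP 5.3), the exclusion (SAP 5.1) and the CGIC clause (Protocol 10.3.1.2). Two assumptions are made. The protocol clause is applied at the flagged visit with the existing CGIC ≥ 5 cut-off, which that clause does not itself repeat. The baseline Ashworth score is not flagged.

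| Finding at the flagged visit | Flags ignored | Visible SAP text | Protocol rule |
|---|---|---|---|
| CGIC ≥ 5, Ashworth increase | meets criterion | cannot meet it | meets criterion |
| CGIC ≥ 5, no Ashworth increase | does not | cannot meet it | meets criterion |
| CGIC < 5 | does not | cannot meet it | does not |

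The documents give opposite answers in the first two rows. The protocol synopsis counts failure at any Part 3 visit, so a subject's overall status differs only when no unflagged visit meets the criterion. For a fixed set of PP subjects, the failure count under the SAP text is therefore no larger than the count ignoring flags, which is no larger than the count under the protocol rule. This ordering follows from the definitions and is not evidence of a material effect. It need not hold if a baseline Ashworth score is flagged.

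**2. What the 10% condition counts**

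The two SAP definitions share the conditions on randomisation, dosing and paired scores. PP differs from ITT only by removing subjects with important protocol deviations, so the condition counts those subjects, pooled over arms. The smallest number k that opens it satisfies k / N > 0.10:

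- N = 240 (planned minimum randomised, SAP 3.2.1): 24/240 = 10.0%, not enough; 25/240 = 10.4%, enough. PP must be 215 or smaller.
- N = 230 (assumed, since SAP ITT also needs a paired score): 24/230 = 10.4%, so 24.
- N = 200 (assumed): 21/200 = 10.5%, so 21.

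**3. What the flags count**

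Visits 8 to 11 give 4 scheduled assessments per subject, or 240 × 4 = 960. A flag on any of them does not by itself remove a subject from PP.

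**4. Where flags and exclusions overlap**

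SAP 6.1.3 lists "receiving excluded concomitant medications" as an important deviation and includes more broadly anything that "might significantly affect the completeness, accuracy, and/or reliability of the study data". Protocol 10.5 says that before lock "any major protocol violations, including changes in medication use or physiotherapy, and changes in medical condition will be identified". The causes of flagging can therefore also be grounds for removal from PP. Whether they are in a given case is left to the deviation review in SAP 6.1.3 and the blinded review in SAP 5.5. Flags move the 10% condition only through that ruling.

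The documents give no flag frequency, so no shift in failure rates can be calculated.

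**The case against.** **Silence is not repeal.** SAP 2 presents the SAP as an elaboration of the protocol and overrides it only on a discrepancy. SAP 5.6 refers to carrying out the analyses in both documents. On that reading the CGIC clause survives and nothing changes. This is arguable, but SAP 5.6 sets the conditions before analysis starts and does not say how a visit is scored. SAP 5.1 restates the protocol's exclusion and ends before the clause. At best the two texts are ambiguous.

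**Redaction.** Parts of SAP 6.2.1.3 to 6.2.1.6 and the sensitivity analyses (a) to (d) in Protocol 10.4.3.2.1 cannot be read. A scoring rule, or a separate analysis of confounded visits, could be there. This stands and limits confidence.

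**The 10% condition comes from the protocol.** A reader might infer that the SAP introduced it. It did not; it is in the synopsis and Protocol 10.3.1.2. Only the CGIC clause is a difference between the documents. Running the analysis unconditionally is a recommended improvement, not the repair of a conflict.

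**Overlap.** Seriously confounded subjects may leave PP altogether and so help to open the condition. This is right, and it means that flags and PP size are not independent. The scoring question then concerns only flagged visits in subjects who remain in PP.

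**There is a process.** SAP 5.5 sends populations, missing data and confounding to a signed blinded review. That protects against unblinded choices, but it leaves a known scoring rule to meeting minutes when the protocol had already written one.

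**Conclusion.** The point holds as a minor one, with medium confidence. The visible texts differ on scoring a PP visit whose Ashworth score is set aside. If the SAP governs, such visits default to non-failure. The condition on running the analysis needs at least 25 of 240 subjects with important deviations and does not count flagged assessments as such, so the only visible analysis that sets confounded scores aside may not run.

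Three stronger readings are not supported:

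- The primary result is not affected. Both rules belong to the PP analysis; the primary analysis uses ITT.
- It cannot be said that the SAP text shrinks or exaggerates the treatment difference. It can lower failure counts within an arm, but the effect on the difference depends on how flags fall by arm, which the documents do not give.
- It cannot be said that confounding is otherwise ignored. Protocol 10.4.3.4.2 plans subgroups by use of neurological concomitant medication, although the visible text there does not set any score aside.

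The conclusion rests on the visible SAP 5.1 being complete at that sentence, on the protocol clause applying visit by visit, and on failure at any Part 3 visit counting.

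**What to change.** 1. In SAP 5.1, restore the Protocol 10.3.1.2 rule: at a flagged visit, PP response status rests on CGIC alone, using the existing cut-off of 5 or more. If another rule is preferred, state and justify it, so that excluded visits do not default to non-failure.
2. In SAP 5.1 and 6.2.1.6, run the analysis that excludes confounded assessments whether or not the 10% condition is met, and label it supportive.
3. Report the number of flagged visits by arm.

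The cost is a few SAP sentences and one extra supportive table, using information already collected in the blinded review. Because SAP 2 gives the SAP precedence, the edit can stay within the SAP. The main drawback is that CGIC alone is a looser criterion than the two-part one and may be confounded by the same events. PP also removes subjects after randomisation. Both are reasons to keep the result supportive.
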